4.2.2. Adherence to Study Drug

The total amount of study drug administered (mg) will be summarized using descriptive statistics.

For tirabrutinib and idelalisib, the presumed total number of doses administered to a subject will be determined by the data collected on the drug accountability CRF using the following formula:

Total Amount of Study Drug Administered (mg) =

$$\left(\sum \text{No. of Doses Dispensed} \times \text{strength} \right) - \left(\sum \text{No. of Doses Returned} \times \text{strength} \right)$$

The level of on-treatment adherence to the study drug regimen will be determined by the total amount of study drug administered relative to the total amount of study drug expected to be administered during a subject's actual on-treatment period based on the study drug regimen. Investigator-prescribed interruption, reductions and escalations as specified in the protocol will be taken into account. If there are treatment periods that bottles are not returned or the return information is missing, these periods will be excluded from the on-treatment adherence calculation for both total amount of study drug administered and study drug expected to be administered. If subjects never returned any bottle, the adherence will be set as missing.

The level of on-treatment adherence will be expressed as a percentage using the following formula:

$$\text{On-Treatment Adherence (\%)} = \left(\frac{\text{Total Amount of Study Drug Administered}}{\text{Study Drug Expected to be Administered on Treatment}} \right) \times 100$$

Descriptive statistics for the level of on-treatment adherence with the number and percentage of subjects belonging to adherence categories (eg, < 75% and ≥ 75%) will be provided by treatment group for the Safety Analysis Set.

A by-subject listing of study drug administration and drug accountability will be provided separately by subject ID number (in ascending order) and visit (in chronological order).

4.3. Protocol Deviations

Subjects who did not meet the eligibility criteria for study entry but enrolled in the study will be summarized regardless of whether they were exempted by the sponsor or not. The summary will present the number and percentage of subjects who did not meet at least 1 eligibility criterion and the number of subjects who did not meet specific criteria by treatment group based on the All Enrolled Analysis Set. A by-subject listing will be provided for those subjects who did not meet at least 1 eligibility (inclusion or exclusion) criterion. The listing will present the eligibility criterion (or criteria if more than 1 deviation) that subjects did not meet and related comments, if collected.

Protocol deviations occurring after subjects entered the study are documented during routine monitoring. The number and percentage of subjects with important protocol deviations by deviation reason (eg, nonadherence to study drug, violation of select inclusion/exclusion criteria)

will be summarized by treatment group for the All Enrolled Analysis Set. A by-subject listing will be provided for those subjects with important protocol deviation.

4.4. Assessment of COVID-19 Impact

This study was ongoing during the novel coronavirus (2019 nCoV [COVID-19]) pandemic, and the COVID-19 pandemic has caused a disruption in the regular visit schedules for this study. Some subjects were unable to attend onsite visits due to shelter in place guidelines, site closures, or other reasons. This section provides how to handle special situations due to COVID-19 in the analysis.

Adverse events (AEs) due to COVID-19 will be included in AE analyses if applicable. A by-subject listing of Adverse Events due to COVID-19 may be provided. The COVID-19 Standardized MedDRA Queries (SMQ) with Broad Scope in [Appendix 2](#) will be implemented.

4.4.1. Study Drug or Study Discontinuation Due to COVID-19

A by-subject listing of reasons for premature study drug or study discontinuation due to COVID-19 will be created.

4.4.2. Protocol Deviations Due to COVID-19

A by-subject listing will be provided for subjects with important protocol deviation related to COVID-19. A separate listing will be provided for subjects with non-important protocol deviation related to COVID-19.

4.4.3. Missed and Virtual Visits Due to COVID-19

A by-subject listing of subjects with missed or virtual visits due to COVID-19 will be provided by subject ID number in ascending order .

Information regarding virtual or missed visits due to COVID-19 was collected as free text in the CRF comment fields. The determination of missing or virtual visits due to COVID-19 was done using Natural Language Processing (NLP) to search the CRF comment fields. A detailed explanation of the algorithm is given in [Appendix 3](#).

5. BASELINE CHARACTERISTICS

5.1. Demographics

Subject demographic variables (ie, age, sex, race, and ethnicity) will be summarized by treatment group and overall using descriptive statistics for age, and using number and percentage of subjects for sex, race, and ethnicity. The summary of demographic data will be provided for FAS.

A by-subject demographic listing, including the informed consent date, will be provided by subject ID number in ascending order.

5.2. Other Baseline Characteristics

Other baseline characteristics include body weight (in kg), height (in cm), body mass index (BMI; in kg/m²), Eastern Cooperative Oncology Group (ECOG) Performance Status, CIRS (Cumulative Illness Rating Scale), fluorescence in situ hybridization (FISH) results, TP53 mutation status, and IGHV mutation status. These baseline characteristics will be summarized by treatment group and overall using descriptive statistics for continuous variables and using number and percentage of subjects for categorical variables. The summary of baseline characteristics will be provided for FAS. No formal statistical testing is planned.

A by-subject listing of other baseline characteristics will be provided by subject ID number in ascending order.

5.3. Medical History

Medical history will be collected at screening for disease-specific and general conditions (ie, conditions not specific to the disease being studied).

Disease-specific medical history will be summarized by treatment group and overall by the number and percentage of subjects with each prepopulated condition. The summary will be provided for FAS. Time since CLL diagnosis (years) will be calculated by (date of first dose of study drug – date of CLL diagnosis) / 365.25. Time since CLL diagnosis will be summarized using summary statistics for a continuous variable. Disease stage at diagnosis and at screening and cytogenetic risk group will be summarized using summary statistics for a categorical variable. No formal statistical testing is planned. A by-subject listing of disease-specific medical history will be provided by subject ID number in ascending order.

In deriving the time since CLL diagnosis, all partial dates of diagnosis and last regimen will be identified, and the partial dates will be imputed as follows:

- If day and month are missing but year is available, then the imputed day and month will be 01 Jan.
- If day is missing but the month and year are available, then the imputed day will be the first day of the month.
- Partial date will not be imputed if the year is missing.

General medical history data will not be coded, but will be listed only. A by-subject listing of general medical history will be provided by subject ID number in ascending order.

5.4. Prior Anti-cancer Therapy

Number of prior regimens, time since the completion of last regimen, and time since progression in the last regimen will be summarized by treatment group using descriptive statistics based on FAS. A partial completion date will be imputed using the algorithm defined in Section 5.3.

The regimens and prior therapies that the subjects received will be summarized. The last regimen subjects received prior to study entry and the best response and PD to the last regimen will be summarized.

Number of subjects who received prior radiation therapy and surgery will be listed.

6. EFFICACY ANALYSES

Efficacy analysis will be performed on FAS. The result summary will be provided by treatment group if not otherwise specified.

6.1. Primary Efficacy Endpoint

6.1.1. Definition of the Primary Efficacy Endpoint

The primary efficacy endpoint of this study is the rate of CR per modified IWCLL 2008 criteria {Hallek 2008} at Week 25, which is defined as the proportion of subjects who achieved CR/CRi at Week 25. Subjects who received anti-cancer therapy other than the study drug prior to achieving CR/CRi at Week 25, will be considered as nonresponders for CR/CRi and will be included in the denominator when calculating the CR rate at Week 25.

The analysis window of Week 25 response assessment is defined as $24 \times 7 \pm 28$ days (inclusive) starting from first dose. This analysis window is extended from the visit window to capture the assessments outside the scheduled window. If there are multiple assessments within the analysis window, records will be chosen based on rules specified in Section 3.8.3.

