6.2.13. Bone Marrow Assessment

For subjects without radiographic evidence of disease at screening, a bone marrow biopsy including aspirate is required within the screening window.

A bone marrow biopsy including aspirate is required at Week 25 for subjects who otherwise would meet criteria for a CR or complete remission with incomplete bone marrow recovery (CRi).

An additional bone marrow biopsy, including aspirate, may be obtained on protocol per investigator discretion following evidence of an improvement in clinical response.

Any bone marrow aspirate obtained should be sent for central MRD assessment, immunophenotyping, bio-banking, and follow-up research.

CCI

[REDACTED]

CCI

[REDACTED]

CCI

[Redacted]

[Redacted]

[Redacted]

[Redacted]

[Redacted]

[Redacted]

[Redacted]

CCI

[Redacted]

[Redacted]

CCI [REDACTED]	[REDACTED]	
[REDACTED]	[REDACTED]	

[REDACTED]

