8.1.2. Primary Endpoint

The primary endpoint is the rate of CR per modified IWCLL 2008 criteria {Hallek 2008} at Week 25.

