8.1.3. Secondary Endpoints

The secondary endpoints of this study are:

- Rate of CR/BM MRD- at Week 25
- Rate of CR/PB MRD- at Week 25
- ORR at Week 25 including CR, CRi, PR, and PR with lymphocytosis
- Type, frequency, and severity of AEs and SAEs

CCI

[REDACTED]

[REDACTED]

[REDACTED]

[REDACTED]

[REDACTED]

[REDACTED]

[REDACTED]

[REDACTED]

[REDACTED]

[REDACTED]

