8.5. Efficacy Analysis

8.5.1. Primary Endpoint

Tumor response will be based on investigator's assessment according to the modified IWCLL 2008 criteria (see [Appendix 6](#)).

Rate of CR will be calculated by treatment arms using the FAS. The 2-sided 90% exact confidence interval (CI) of CR will be estimated using the Clopper-Pearson method.

No inferential test will be performed. The goal of this analysis is to obtain preliminary estimates of the CR rate.

In addition, the analysis of the primary endpoint will be performed using the PP analysis set.

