8.9. Sample Size

The primary goal of the study is to evaluate the efficacy of the combination treatment described above. The evaluation will be based on the estimation of the CR rate and its corresponding exact confidence interval for each arm. Approximately 30 subjects will be enrolled into Arm B, which will result in the 90% confidence interval of the observed CR rate to be within $\pm 17.0\%$. The 90% confidence interval for a given observed CR rate is shown in the table below.

Table 8-1. 90% Confidence Intervals at Different CR Rates

Sample Size	CR Rate	95% Confidence Interval using Clopper-Pearson Method
30	20%	(9.1%, 35.7%)
30	30%	(16.6%, 46.5%)
30	40%	(25.0%, 56.6%)
30	50%	(33.9%, 66.1%)
30	60%	(43.4%, 75.1%)

With Amendment 3, randomization was discontinued. All subsequently enrolled subjects will enter Arm B. A total of approximately 6 subjects in Arm A and 30 subjects in Arm B will be enrolled, thus the total sample size for the study will be approximately 36 subjects.

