Appendix 6. Modified IWCLL 2008 Response Criteria

The determination of CLL response and progression will be based on standardized International Workshop on CLL (IWCLL) 2008 criteria {Hallek 2008}, as specifically modified for this study to reflect current recommendations which consider the mechanism of action of small molecule targeted therapy {Cheson 2012}.

Complete remission (CR):

All below listed criteria must be fulfilled and no disease related symptoms should be present.

Complete remission with incomplete recovery of the bone marrow (CRi):

All below listed criteria must be fulfilled, except for an incomplete recovery of the bone marrow with persisting anemia, thrombocytopenia and/or neutropenia (related to toxicity of treatment and not due to CLL) and no disease related symptoms should be present.

Partial response (PR):

Among the below listed criteria at least 2 from group A and 1 from group B must be fulfilled.

Partial response with lymphocytosis (PR-L):

Among the below listed criteria at least 2 from group A and 1 from group B must be fulfilled, however, a lymphocytosis related to treatment may be present.

Nodular partial response (nPR):

All criteria for a CR/CRi are fulfilled, but the bone marrow shows lymphoid nodules. As in a lot of cases these nodules are related to bone marrow proliferation during recovery, efforts should be made to prove that these lymphocytes are no CLL cells by 4-colour-flow cytometry to be able to define these patients as CR/CRi. If this cannot be proved by either FACS or MRD from the bone marrow patients will be considered PR and therefore this category will not appear on the eCRF.

Stable disease (SD):

Failure to achieve a PR and absence of PD.

Progressive disease (PD):

Presence of at least 1 of the below enlisted criteria or appearance of new lymph nodes > 1.5 cm, hepato- or splenomegaly or organ infiltration by CLL.

Response criteria

Parameter	CR	CRi	PR	PR-L	PD
Group A (indicating tumor load)					
Lymphadenopathy ¹	none > 1.5 cm		decrease \geq 50%		increase by \geq 50% or new lymph nodes \geq 1.5 cm
Hepatomegaly	none		decrease \geq 50%		Increase by \geq 50 %
Splenomegaly	none		decrease \geq 50%		Increase by \geq 50 %
Blood lymphocytes	< 4000/ μ L		decrease of \geq 50% from baseline	increase	Increase by \geq 50% over baseline ² to \geq 5000/ μ L
Bone marrow	Normocellular	hypocellular	50% reduction in BM infiltrates ³		irrelevant
	30% lymphocytes, no B-lymphoid nodules				

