1.3. Sample Size and Power

The primary goal of this study is to evaluate the efficacy of the combination of tirabrutinib and idelalisib with obinutuzumab in relapsed and refractory CLL. The evaluation will be based on the estimation of the CR rate (including CR and CR with incomplete recovery of the bone marrow (CRi)) and its corresponding exact confidence interval. Approximately 30 subjects will be enrolled into Arm B, which will result in the 90% confidence interval (CI) of the observed CR rate to be within $\pm 17.0\%$. The 90% CI for a given observed CR rate is provided in [Table 1-1](#).

Table 1-1. 90% Confidence Intervals at Different CR Rates

Sample Size	Observed CR Rate	90% Confidence Interval using Clopper-Pearson Method
30	20%	(9.1%, 35.7%)
30	30%	(16.6%, 46.5%)
30	40%	(25.0%, 56.6%)
30	50%	(33.9%, 66.1%)
30	60%	(43.4%, 75.1%)

With Amendment 3, randomization was discontinued. All subsequent subjects will be enrolled to Arm B. A total of approximately 6 subjects in Arm A and 30 subjects in Arm B will be enrolled, thus the total sample size for the study will be approximately 36 subjects.

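### The SAP's primary CR rate counts CRi as success where the protocol names CR; the visible text does not declare the change and plans no CR-only estimate

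*SAP*

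**What the plan says.** **Protocol.** Section 8.1.2 states: "The primary endpoint is the rate of CR per modified IWCLL 2008 criteria", assessed at Week 25. The synopsis agrees, and 8.5.1 carries the same term into the analysis: "Rate of CR will be calculated by treatment arms using the FAS". The two MRD endpoints in 8.1.3 are likewise named for CR, combined with marrow or blood MRD negativity. CRi appears in the same list only under overall response: "ORR at Week 25 including CR, CRi, PR, and PR with lymphocytosis". Appendix 6 defines CRi separately from CR: "All below listed criteria must be fulfilled, except for an incomplete recovery of the bone marrow with persisting anemia, thrombocytopenia and/or neutropenia". It adds that the cytopenia must come from treatment toxicity and not from the leukaemia, and that no disease-related symptoms may be present.

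**SAP.** Section 6.1.1 repeats the protocol's endpoint name and then adds the definition: "which is defined as the proportion of subjects who achieved CR/CRi at Week 25". Section 6.2 uses CR/CRi in both MRD endpoints. Section 6.1.2 plans one primary estimate, called the CR rate, with a two-sided 90% Clopper-Pearson interval. Section 6.2.2 adds a by-subject listing of overall response.

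**The concern.** The SAP changes which subjects count as successes while keeping the protocol's name for the result. A reader who meets a CR rate in the report, and looks to the protocol for its meaning, will take it as CR without CRi.

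The protocol plans no inferential test and says the aim of the primary analysis is a preliminary estimate of the CR rate (8.5.1). The estimate is therefore the result, and an unclear definition goes straight to its meaning. Counts of CR also carry weight in this programme: protocol 1.5 gives 0 CRs among 10 evaluable CLL subjects on the doublet as the reason for closing Arm A. Response is judged by the investigator in an open-label study without an adjudication committee (8.5.1, 8.11), which makes a fixed and clearly labelled definition more important.

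**Working it through.** **1. What the protocol means by CR.** It never says CR only, so this has to be inferred.

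- Appendix 6 gives CR and CRi separate definitions and separate table columns. CR requires a normocellular marrow and minimum platelet, hemoglobin and neutrophil values. For CRi the marrow is hypocellular and the three blood counts are marked as irrelevant.
- Where the protocol wants both categories, it names both: in ORR (8.1.3), in the Week 25 marrow requirement (6.2.13), and in footnote 16 of the Study Procedures Table.
- The primary endpoint and the MRD endpoints name CR alone.

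The natural reading is CR without CRi.

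**2. Where the SAP changes it.** The sample-size sections show the insertion most clearly.

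| Item | Protocol | SAP |
|---|---|---|
| Sample-size basis | 8.9: "The evaluation will be based on the estimation of the CR rate and its corresponding exact confidence interval for each arm" | 1.3: "estimation of the CR rate (including CR and CR with incomplete recovery of the bone marrow (CRi)) and its corresponding exact confidence interval" |
| Primary endpoint | 8.1.2: CR | 6.1.1: CR/CRi |
| CR with marrow MRD negativity | 8.1.3: CR | 6.2: CR/CRi |
| CR with blood MRD negativity | 8.1.3: CR | 6.2: CR/CRi |
| ORR | 8.1.3: CR and CRi listed separately | 6.2: CR and CRi listed separately |

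**3. Whether it is declared.** SAP 6.4 is where changes to the protocol's efficacy analyses belong. Its visible text adds ORR by best response and time to clinical response, and does not mention CRi. One line there and a block after 6.2.2 are redacted, so this holds for the visible text only.

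**4. The plan's own figures.** For x successes in n subjects, the 90% Clopper-Pearson limits are:

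- lower = the 0.05 quantile of Beta(x, n − x + 1)
- upper = the 0.95 quantile of Beta(x + 1, n − x)
- for x = 0 the lower limit is 0 and the upper limit is 1 − 0.05^(1/n)

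With n = 30 and x = 6, 9, 12, 15 and 18, these give 9.1 to 35.7, 16.6 to 46.5, 25.0 to 56.6, 33.9 to 66.1, and 43.4 to 75.1 (in %). All five agree with SAP Table 1-1. Over every x at n = 30, the largest distance from estimate to limit is 16.6 points, so the stated precision of ±17.0% also holds. These figures depend only on x and n and are valid under either definition.

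**5. Effect of counting CRi.** With k CRi subjects the estimate moves from x/n to (x + k)/n, a shift of k/n. For one CRi that is 1/30 = 3.3 points in Arm B and 1/6 = 16.7 points in Arm A. The documents give no CRi rate, so k = 0 to 3 is an assumption.

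| CR in Arm B (of 30) | CR alone, % (90% CI) | CR/CRi with k = 3, % (90% CI) |
|---|---|---|
| 0 | 0.0 (0 to 9.5) | 10.0 (2.8 to 23.9) |
| 3 | 10.0 (2.8 to 23.9) | 20.0 (9.1 to 35.7) |
| 6 | 20.0 (9.1 to 35.7) | 30.0 (16.6 to 46.5) |

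From 6 CRs, the intermediate values are 23.3% (11.5 to 39.4) for k = 1 and 26.7% (14.0 to 43.0) for k = 2. With k = 0 the definitions agree.

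**6. Whether k above 0 is plausible.** Protocol 1.5.1 reports neutropenia of Grade 3 or higher attributed to treatment in 6 of 23 subjects on the doublet. Section 1.4 reports Grade 3 or higher neutropenia in 28% of 32 subjects given idelalisib with obinutuzumab, at a higher idelalisib dose and in untreated disease. Neither is a CRi rate; they show only that a few CRi responses would be no surprise.

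**The case against.** The best reply is that the SAP settles an ambiguity and does not depart from the protocol. Nothing in the protocol excludes CRi from the rate of CR, CRi is by name a form of complete remission, and Appendix 6 in places writes the two together as CR/CRi. The SAP gives its definition in 1.3, 6.1.1 and 6.2, so nothing is hidden. CRi relaxes marrow cellularity and blood counts, and only for cytopenia due to treatment; the node, liver, spleen and blood-lymphocyte criteria stay the same. The MRD endpoints still require MRD negativity. The by-subject listing allows CR alone to be counted by hand, and one sentence in 6.4 with a clearer label would close the gap.

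Part of this stands. The definition is open, the harm is limited to interpretation, and the size is hypothetical. The SAP's revision table is weak evidence either way, because it records edits to the SAP and need not list departures from the protocol. Arm A matters less, since the primary objective concerns the obinutuzumab combination.

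The ambiguity argument does not carry. The joint CR/CRi wording in Appendix 6 belongs to the rule for lymphoid nodules in the marrow and does not merge the categories; it shows that a combined term was at hand and was not used for the endpoint. A listing is also not a planned estimate with an interval.

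**Conclusion.** The concern holds. The SAP reports under the protocol's CR label a rate that can only equal or exceed the rate of CR, in the primary endpoint and in both MRD endpoints. The visible text neither declares the change in 6.4 nor plans CR alone as an estimate.

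The size is 3.3 points per CRi in Arm B, so 0 to 10 points over the assumed 0 to 3 CRi. There is no type I error or power consequence because nothing is tested. This should be fixed, because it bears on the meaning of the one number that the primary analysis exists to produce. The conclusion rests on reading the protocol's CR as excluding CRi, and on the unredacted text for both absences.

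**What to change.** In SAP 1.3, 6.1.1 and 6.2, define success as CR alone, in line with protocol 8.1.2. For the primary endpoint and both MRD endpoints, add a supportive row labelled CR/CRi with the same 90% Clopper-Pearson interval, and record it in SAP 6.4.

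If the team intends CR/CRi as the primary endpoint, amend the endpoint wording in the protocol synopsis and 8.1.2 (Appendix 6 can stay as it is), declare the change in SAP 6.4, call the result the CR/CRi rate, and still show CR alone.

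The first route costs some SAP wording and one extra row per response table. It needs no new data, because the response criteria already separate the two categories, though the headline rate may be slightly lower. The second route also needs a protocol amendment.
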